9.2.2. Operative (Surgery)

All subjects will undergo cataract surgery with implantation of the Vivity IOL. The surgeon's usual standard of care with regard to treatment and medication will be used for all study subjects. Surgery planning and IOL power calculation will be performed using the surgeon's preferred method preoperatively and remeasured with the Optiwave Refractive Analysis (ORA) system intraoperatively, with an

initial a-constant provided by Alcon. The implanted lens power will be based on which assessment the surgeon is most confident with.

Surgical findings will be recorded and any adverse events/serious adverse events (AEs/ SAEs) occurring during surgery will be noted at this visit. Any other problems during surgery and comments regarding surgery will be documented.

Any subject whose surgery is not completed successfully will be documented in the appropriate case report form. These subjects will be monitored for safety but clinical performance data may be excluded from the analysis.

9.2.3. Postoperative 1 Day

All routine, usual standard of care postoperative measures should be undertaken. In addition, the subject will undergo VA testing in accordance with the specifications below (Section 9.3). Adverse events will be monitored.

9.2.4. Postoperative 1 Week

All routine, usual standard of care postoperative measures should be undertaken. In addition, the subject will undergo a manifest refraction and VA testing (Section 9.3). Any device deficiencies or adverse events will be monitored.

9.2.5. Postoperative 1 Month

All routine, usual standard of care postoperative measures should be undertaken. In addition, the subject will undergo a manifest refraction and VA testing (Section 9.3). Any device deficiencies or adverse events will be monitored.

9.2.6. Postoperative 3 Months

All routine, usual standard of care postoperative measures should be undertaken. In addition, the subject will undergo a manifest refraction, VA testing and complete the QUVID and IOLSAT questionnaires (Section 9.3). Any device deficiencies or adverse events will be monitored.

9.2.7. Exit Procedures

In the event of premature exit from the study, all study related examinations should be completed where possible. The Exit CRF should be completed, noting that the subject did not complete the study and the reason for premature study exit. If no premature exit from the study occurs, the Exit CRF should be completed at the end of Visit 6 (Postoperative 3 Months).

9.3. Study Methods and Measurements

All routine testing and basic eye examinations should be carried out at each study visit. Abnormalities should be recorded in the CRF “Comment” section. Specific study examination procedures are outlined below.

9.3.1. Manifest Refraction

Perform a manifest refraction with a high contrast logMAR chart under photopic lighting conditions ($>85 \text{ cd/m}^2$). Document refraction results with sphere, cylinder and axis readings. If uncorrected visual acuity is not improved by manifest refraction, use zero for sphere and cylinder and draw a line through the blank for the axis.

Note: Each subject should be manually refracted to his/her best correction by an ophthalmologist, optometrist, or a skilled technician using a phoropter or trial lenses.

9.3.2. Visual Acuity (VA)

To obtain logMAR VA, ask subjects to begin reading the chart at the smallest row where all letters are easily distinguishable. Have subjects continue to read rows with smaller letters and encourage subjects to guess at all letters in a line if at least one correct response was given on the previous row. Request subjects read rows until no letters on a row are read correctly or until all letters on a row are too indistinguishable to even be guessed.

While the subject is reading the chart, record the number of letters on each line read incorrectly by the subject. The last line from which the subject read at least one letter correctly is recorded as the baseline logMAR VA. The actual logMAR VA is calculated using the baseline logMAR VA line and the number of letters read incorrectly. This VA should be recorded as the best-corrected monocular visual acuity at distance.

It is sufficient to record the uncorrected VA at distance only for the 1-day visit.

Postoperatively conduct testing uncorrected at all visits. In addition, conduct testing with the manifest distance refraction in place at 1 week, 1 month, and 3 months post-operatively.

Distance VA

Measure distance visual acuity using a high contrast logMAR ETDRS chart under photopic lighting ($>85 \text{ cd/m}^2$) at a distance of 6 m.

Intermediate VA

Have the subject view an appropriately-scaled high-contrast logMAR ETDRS Visual Acuity Chart at 66 cm. Visual acuity determined with the chart will be recorded and scored.

Near VA

Conduct near testing with an appropriately-scaled logMAR ETDRS Visual Acuity Chart at 40 cm. Visual acuity determined with the chart will be recorded and scored.

Low Contrast Distance VA

Measure distance visual acuity using a low contrast (25%) logMAR ETDRS chart under photopic lighting (>85 cd/m²) at a distance of 6 m.

9.3.3 Questionnaires

The patient satisfaction (IOLSAT) questionnaire and the visual disturbance (QUVID) questionnaire, related to quality of vision, will be administered to subjects at the 3-month visit. The administrator should ensure the subjects understand the nature of the questions but should not interpret them for the subject.

9.4. Unscheduled Visits

Unscheduled exams may be conducted at the discretion of the Investigator with all relevant information from the exam recorded in the source documents and on the Unscheduled Visit pages within the CRF booklet.

9.5. Discontinued Subjects

Discontinued subjects are those who do not have an exit visit or who come into the office to be exited prior to the scheduled final study visit. Subjects may be discontinued from the study at any time if, in the opinion of the investigator, their continued participation in the study poses a risk to their health. The reasons for discontinuation include:

- a. Adverse event;
- b. Lost to follow-up;
- c. Subject decision unrelated to an adverse event;
- d. Protocol violation;
- e. Treatment failure;
- f. Other.

To ensure the safety of all subjects who discontinue prior to Visit 6, investigators should assess each subject and, if necessary, advise them of any therapies and/or medical procedures that might be needed to maintain their health. Any changes in medical health and/or use of concomitant medications should also be captured.

10. ANALYSIS PLAN***10.1. Analysis Data Sets***

All subjects who are enrolled in the study will be evaluated for safety. Efficacy analyses will be performed based on data from those eyes where uncomplicated cataract surgery with Vivity IOL implantation was completed.

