10.2. Statistical Methodology

A summary of the data will be prepared for all measurement time points. Summaries of the changes observed between the 1 month and 3 month post-operative visits will also be summarized.

For variables measured on a continuous scale, these summaries will include the sample size, as well as the mean, standard deviation, median, minimum, and maximum. For variables measured on a categorical scale, summaries will provide the number and percentage of subjects who provided each score (or change in scores). These summaries will be provided for all eyes completing the study.

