15. STANDARD EVALUATION PROCEDURES

Table 15.1. Proposed Visits and Study Assessments

(visits are by patient, with both eyes tested)

Activity	Pre-operative	Operative	Postoperative			
	Visit 1	Visit 2	Visit 3	Visit 4	Visit 5	Visit 6
			1 Day	1 Week	1 Month	3 Months
Informed Consent	X					
Demographics	X					
General Information: Medical History	X					
Surgery		X				
Manifest refraction	X			X	X	X
Monocular uncorrected distance VA	X		X	X	X	X
Monocular best corrected distance VA	X			X	X	X
Monocular uncorrected and best distance-corrected intermediate VA				X	X	X
Monocular uncorrected and best distance-corrected near VA				X	X	X
Binocular uncorrected and best-corrected distance VA						X
Binocular uncorrected and best distance-corrected intermediate VA						X
Binocular uncorrected and best distance-corrected near VA						X
Binocular distance corrected low contrast VA						X
IOLSAT Patient Satisfaction Survey						X
QUVID Visual Disturbance questionnaire						X
Monitor for Adverse Events and Device Deficiencies		X	X	X	X	X
Complete Exit Form ¹						X

¹ Complete Exit Form upon termination of subject participation, or at Visit 6, whichever occurs first.

* To be performed if deemed necessary by the investigator

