18. STUDY ENDPOINT CRITERIA

18.1. Patient Completion of Study

If a study patient has completed the final visit (Visit 6) of the study, he/she is considered to have completed the study.

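### Section 9.5 lists an undefined treatment-failure exit reason, and Section 10.2 summarises completers only, so exits related to a poor lens result could flatter the single-arm results

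*Combined protocol and SAP*

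**What the plan says.** Section 9.5 (Discontinued Subjects) states one ground for the investigator to act, a judgement that "their continued participation in the study poses a risk to their health". It then lists six reasons for discontinuation. One is "e. Treatment failure", an entry separate from adverse event. The document does not define it. Discontinued subjects include those who "come into the office to be exited prior to the scheduled final study visit".

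Three other parts of the document decide what happens to such a subject's data:

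- **Schedule.** Table 15.1 places "Binocular uncorrected and best-corrected distance VA" at Visit 6 only. The same holds for binocular intermediate and near acuity, low-contrast acuity, IOLSAT and QUVID.
- **Completion.** Section 18.1 says: "If a study patient has completed the final visit (Visit 6) of the study, he/she is considered to have completed the study". Section 9.2.7 has the Exit CRF record anyone who leaves early as not having completed. It asks for the study examinations at exit where possible.
- **Analysis set.** Section 10.1 says: "Efficacy analyses will be performed based on data from those eyes where uncomplicated cataract surgery with Vivity IOL implantation was completed". Section 10.2 says of its descriptive summaries: "These summaries will be provided for all eyes completing the study".

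**The concern.** The endpoints of this study are measures of how well a permanently implanted lens performs: acuity, prediction error, visual disturbance and satisfaction. If treatment failure means a poor result on any of these, the reason for leaving the study is the outcome under study. The study is unmasked, and monocular acuity and refraction are known at 1 week and 1 month, so an exit could follow a disappointing early result. The subject would then have no scheduled primary measurement and would fall outside the completers' summary.

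Such selection runs in one direction. It would improve the mean acuities, the percentage of eyes within 0.5 D and the satisfaction scores. The synopsis states that the lens gives good results at 3 months in long eyes, and a single-arm design has no comparator in which the same selection would occur.

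**Working it through.** **1. Following a subject through the text.** Suppose a subject leaves at 1 month with treatment failure recorded as the reason.

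- Under 9.5 the subject is discontinued, and under 9.2.7 and 18.1 is not a completer.
- The one exception to the completion rule, in 18.3, is for a severe adverse event that may be related to the study. It does not cover treatment failure.
- Binocular acuity, QUVID and IOLSAT have not been scheduled before the exit. If they are done at the exit visit, they fall outside the 3-month window unless the exit is at day 90 − 20 = 70 or later (Table 9.2-1).
- Under 10.2 as worded, the subject's 1-week and 1-month data are also left out. Under 10.1 they would be kept.
- Section 18.2 replaces only subjects lost before surgery, and no missing-data method is stated.

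**2. The plan's own figure.** Section 11 gives n = 20, SD 0.1 logMAR and a two-sided 95% t interval.

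Half-width = t(0.975, 19) × SD / √n = 2.093 × 0.1 / √20 = 0.0468, which rounds to the stated 0.05. The figure is reproduced.

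With unreplaced losses it becomes 0.0482 at n = 19, 0.0497 at n = 18 and 0.0514 at n = 17. Precision hardly changes, so the width of the interval would not reveal the problem.

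**3. Shift in the mean (illustration).** Let k of 20 implanted subjects leave, on average d logMAR worse than those who stay. Then

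mean of all 20 = mean of completers + (k/20) × d,

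so the completers' mean is too favourable by kd/20. The documents give neither k nor d; both are assumed.

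| k | d = 0.20 | d = 0.30 |
|---|---|---|
| 1 | 0.010 | 0.015 (0.015/0.0468 = 32% of the half-width) |
| 2 | 0.020 | 0.030 (0.030/0.0468 = 64% of the half-width) |

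**4. An extreme case without an assumed gap.** In a simulation with normal data, SD 0.1 and n = 20, exactly the worst 1, 2 or 3 subjects were removed. The mean improved by 0.010, 0.018 or 0.026. The observed SD fell to 0.090, 0.085 or 0.080. Coverage of the nominal 95% interval fell to about 91%, 84% or 74%. This is a severe form of selection, because it assumes that every exit is the worst remaining outcome.

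**5. Eyes within 0.5 D (illustration).** Assume 32/40 = 80.0% of eyes are within range. If 1 subject with both eyes outside leaves, this becomes 32/38 = 84.2%; with 2 such subjects, 32/36 = 88.9%. The starting 32/40 is also assumed.

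**The case against.** The strongest reply is that the list in 9.5 is a set of exit reason codes and not a power to withdraw. It also contains loss to follow-up and subject decision, which are neither investigator decisions nor health risks. It fits the Exit CRF in 9.2.7, which records why a subject left. On this reading the only investigator power in 9.5 is the health-risk one, and the withdrawal rules in 18.2 and 18.3 do not mention treatment failure. This stands as the more natural reading. A reader might infer that the protocol authorises the investigator to remove lens failures; the text does not say so.

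A reader might also take treatment failure to be an efficacy result by definition. The separate entry for adverse event makes that plausible, but the term could equally cover a lens that did not remain in place. The supportable statement is that it is undefined.

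Third, 10.1 is not limited to completers, so it cannot be said that early leavers are certain to be excluded from every efficacy analysis. That is right: 10.1 and 10.2 conflict. But 10.1 cannot supply Visit 6 measurements that were never taken.

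Finally, the sizes are hypothetical. A gap of 0.30 logMAR is three of the plan's own SDs, each shift in the table is smaller than the half-width, and the primary outcome has no performance threshold, so no formal pass/fail decision would change. All of this stands. It limits the weight of the point but does not remove the favourable direction of the bias in the reported estimates.

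**Conclusion.** The point holds in a conditional form. Section 9.5 is wider in its list than in its stated ground, and one listed reason is undefined. If that reason is used for poor lens results, the subject misses the only visit with the primary measurements, and 10.2 leaves the subject out while 10.1 would not. The resulting bias is favourable, with nothing in a single-arm design to offset it.

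Its size cannot be found from the documents. Under the assumed gap of 0.30 logMAR, losing 1 or 2 of 20 subjects shifts the mean by 0.015 or 0.030, against a half-width of 0.047. The documents do not show that such exits are intended or expected. This is a gap in the wording that is cheap to close, not evidence of planned selection.

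**What to change.** 1. In 9.5, reconcile the stated ground with the list of reasons, and define treatment failure or limit it to an exit reason code. Deleting the entry would not be enough: such exits would move to the subject-decision or other category and become harder to see.
2. State that an unsatisfactory visual or refractive result is not in itself a reason to end study follow-up, so that consenting subjects are still assessed at Visit 6.
3. Reconcile 10.2 with 10.1 by summarising, at each visit, all eyes with completed implantation that have data, and not only completers.
4. Report the number of early exits and their reasons.
5. Add a sensitivity summary that includes the exit-examination data collected under 9.2.7.

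These changes concern study follow-up and analysis only, not clinical care. They need protocol wording and slightly more analysis work, with no visits beyond those scheduled. The results may look less favourable.

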10.2. Statistical Methodology

A summary of the data will be prepared for all measurement time points. Summaries of the changes observed between the 1 month and 3 month post-operative visits will also be summarized.

For variables measured on a continuous scale, these summaries will include the sample size, as well as the mean, standard deviation, median, minimum, and maximum. For variables measured on a categorical scale, summaries will provide the number and percentage of subjects who provided each score (or change in scores). These summaries will be provided for all eyes completing the study.

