8. STUDY DESIGN

8.1. Study Design

This study is a single-arm unmasked clinical evaluation study of binocular uncorrected visual acuity at distance (6m), intermediate (66cm) and near (40cm), when implanted in eyes with high ocular axial length (≥ 24.5 mm), after successful bilateral cataract surgery. Subjects will be assessed preoperatively, operatively, and at 1 day, 1 week, 1 month, and 3 months postoperatively. Clinical evaluations will include administration of a visual disturbance questionnaire (QUVID) and a satisfaction questionnaire (IOLSAT), as well as measurement of binocular and monocular visual acuities and manifest refraction.

The primary outcome measure will be the binocular uncorrected visual acuities at distance (6m), intermediate (66cm), and near (40cm), 3 months postoperatively.

Secondary outcome measures are as follows:

- Percentage of eyes with absolute prediction error $\leq 0.5D$ at 3 months postoperatively.
- Monocular and binocular best-distance-corrected visual acuities at distance (6m), intermediate (66 cm), and near (40 cm), 3 months postoperatively.
- Manifest refraction (residual spherical equivalent refraction, residual sphere, and residual astigmatism), 3-months postoperatively.
- Questionnaire for visual disturbance scores (QUVID).
- Patient satisfaction questionnaire scores (IOLSAT).
- Binocular distance corrected low contrast visual acuity (25% contrast) at distance (6m).

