11. SAMPLE SIZE JUSTIFICATION

The distribution of axial length ≥ 24.5 mm in the older population of is $\sim 17\%$.³ As a result, recruitment for qualifying candidates will be limited due to this natural population distribution. It is expected that 20 patients (40 eyes) will provide sufficient data to characterize the clinical performance of the lens. When the sample size is 20, a two-sided 95% confidence interval for a single mean will extend 0.05 from the observed mean, assuming that the standard deviation is known to be 0.1 logMAR and the confidence interval is based on the t-statistic.

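### Does it matter that Section 10.2 lists no confidence interval and summarizes by eye, when the primary acuities are binocular?

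*Combined protocol and SAP*

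**What the plan says.** The primary outcome (Section 8.1) is binocular uncorrected acuity at three distances, 3 months after surgery. Table 15.1 schedules binocular acuity at Visit 6 only.

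Section 11 notes that "recruitment for qualifying candidates will be limited due to this natural population distribution" and then gives the precision: "When the sample size is 20, a two-sided 95% confidence interval for a single mean will extend 0.05 from the observed mean", at an SD of 0.1 logMAR and using the t-statistic.

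For continuous variables, Section 10.2 says that "these summaries will include the sample size, as well as the mean, standard deviation, median, minimum, and maximum". Categorical variables are counted by subject. The section ends: "These summaries will be provided for all eyes completing the study".

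Section 10.1 defines the efficacy set by eye: "Efficacy analyses will be performed based on data from those eyes where uncomplicated cataract surgery with Vivity IOL implantation was completed". On subjects whose surgery is not completed successfully, Section 9.2.2 adds: "These subjects will be monitored for safety but clinical performance data may be excluded from the analysis".

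**The concern.** Three things seem not to fit together.

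- **The interval.** The only quantitative support for 20 subjects is the width of a confidence interval, and no part of Section 10 says that this interval will be reported. The paired tests of Section 10.2.1 compare time points, so they cannot supply inference on a measure taken at one visit.
- **The unit.** A summary over eyes has no meaning for a binocular acuity. If 40 were printed as the n beside a binocular mean, a reader who rebuilt the interval would get one that is about a third too narrow.
- **The one-eye case.** The efficacy set is built from eyes, and the exclusion in Section 9.2.2 is discretionary. No sentence says whether a binocular value counts when only one of the subject's eyes qualifies. The study is unmasked, so the primary n could in principle be settled after results are seen.

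If all three were real, the headline estimates would lack a stated precision, or carry a wrong one, and their denominator would be open to choice.

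**Working it through.** **Inputs.** SD 0.1 logMAR, 95% two-sided, t-based, n = 20 (Section 11); 40 eyes of 20 subjects (Section 7.1).

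**Formula.** Half-width = t(0.975, n−1) × SD / √n.

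**The plan's own figure.** n = 20: 2.0930 × 0.1 / 4.4721 = 0.0468, which rounds to the stated 0.05.

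**Which unit does Section 11 use?** n = 40: 2.0227 × 0.1 / 6.3246 = 0.0320, which rounds to 0.03. The stated figure therefore matches subjects and not eyes. The ratio 0.0320 / 0.0468 = 0.68 is the source of the possible one-third narrowing, and it arises only if the wrong n is printed.

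**Can the interval be obtained from the planned outputs?** It needs n, the mean and the SD. All three are in the Section 10.2 list, and Section 11 gives the method and the confidence level. Section 10.2 says what the summaries include; it does not bar an interval.

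**How much does the one-eye case matter?** The documents give no complication rate. As an illustration, assume that two of the 20 subjects each have one complicated eye. The eye set is then 38, and the primary n is 20 or 18.

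| Primary n | t | Half-width |
|---|---|---|
| 20 | 2.0930 | 0.0468 |
| 18 | 2.1098 | 0.0497 |
| 16 | 2.1314 | 0.0533 |
| 15 | 2.1448 | 0.0554 |

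The rounded 0.05 survives down to n = 16; n = 15 is the first to round to 0.06.

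The choice also affects the mean. If the two subjects differ from the other 18 by d on average, including them shifts the mean by (2/20) × d = 0.1d. With d equal to one SD (0.1, an assumption), the shift is 0.01 logMAR. To move the mean by a full half-width, d would have to be 0.0468 / 0.1 = 0.468 logMAR, or 4.7 SDs.

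**What do the sections say about one-eye subjects?** Section 6 sets the objective in eyes after uneventful surgery. Section 7.2 requires uncomplicated bilateral surgery and applies ocular criteria to both eyes. Section 8.1 places the primary evaluation "after successful bilateral cataract surgery". Section 9.2.2 handles unsuccessful surgery by subject, and Section 18.1 defines completion by patient. Read together, these point to counting a binocular value only when both eyes qualify.

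**The case for a change.** The strongest case for a change is that precision is the study's only quantitative justification, so the interval should be a named output for all three acuities. The closing sentence of Section 10.2 is wrong for binocular data if read literally, and the permissive wording in Section 9.2.2 leaves a choice open in an unmasked study. The remedy would be a few sentences.

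Part of this stands. The interval is not listed, the unit is loosely worded, and no explicit one-eye rule is written. Naming the interval and the unit would be better drafting.

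The consequences do not follow, however. The n = 40 error requires someone to treat 20 readings as 40, which no section instructs. The same closing sentence also covers categorical summaries that Section 10.2 has just counted by subject, which suggests loose phrasing and not a rule about rows. The between-visit tests are limited by their own terms to repeated measures, so they raise no conflict with the primary outcome. Nor was the interval the sole basis for the number: Section 11 begins with limited recruitment. The remaining discretion over one-eye subjects is real but narrow, given how consistently the other sections require bilateral uncomplicated surgery.

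**Conclusion.** No change to the plan is needed. Followed as written, it yields a mean, SD and n for each primary acuity, and the 95% interval follows from these in one line. At the planned 20 subjects the half-width is 0.0468 logMAR, in agreement with Section 11. In the illustrated one-eye case it becomes 0.0497, which rounds to the same stated figure.

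This rests on three assumptions: each binocular value is entered once per subject, the SD is near the protocol's 0.1, and few subjects have only one qualifying eye. The first follows from the nature of the measurement. The other two cannot be checked from the documents, but the half-width still rounds to 0.05 with up to four subjects lost. The study is single-arm and descriptive, with no performance threshold, so no decision depends on the difference. What remains is missing detail that a competent analyst would supply in the way Section 11 already implies.
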